6.3.6 North Star Ambulatory Assessment and 10-Meter Walk/Run Time

Ambulatory subjects will complete the NSAA and 10MWRT. All observed values will be listed.

6.3.7 Pulmonary Function Testing

Pulmonary function tests (PFTs) will measure SVC, FVC, FEV₁, PEF, MIP, MEP, PCF, and IFR. All observed values will be displayed in subject listings.

Observed absolute values and changes from baseline will be summarized for FVC, PEF, and IFR. Percent predicted and changes from baseline will be summarized for FVC and PEF.

Using the model defined in Section 6.1, the comparisons of interest will be the contrasts between CAP-1002 and placebo at Months 3, 6, 9, and 12 for change from baseline in the following parameters:

- FVC, absolute value and percent predicted
- PEF, absolute value and percent predicted
- IFR, absolute value

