7.2.3. Exploratory Endpoints

The **exploratory efficacy endpoints** include the change from baseline to each assessment timepoint for the following assessments:

- All subjects
 - High-level (shoulder) dimension of the PUL 1.2

- High-level (shoulder) dimension of the PUL 2.0
- Mid-level (elbow) dimension of the PUL 2.0
- Distal-level (wrist and hand) dimension of the PUL 1.2
- Distal-level (wrist and hand) dimension of the PUL 2.0
- Grip strength
- Key and tip-to-tip pinch strength
- Elbow flexion strength
- Slow vital capacity (SVC), forced expiratory volume in one second (FEV₁), forced vital capacity (FVC), peak expiratory flow (PEF), maximum inspiratory pressure (MIP), maximum expiratory pressure (MEP), peak cough flow (PCF), and inspiratory flow reserve (IFR)
- Left ventricular structure and function as assessed by cardiac MRI including ejection fraction, end-diastolic volume, end-systolic volume, stroke volume, regional wall thickness, and circumferential strain
- Biomarkers may include those for muscle inflammation (osteopontin); systemic inflammation (interleukin 1 beta [IL-1 β], IL-2, -6 and -10; tumor necrosis factor alpha [TNF- α] and C-X-C motif chemokine 10 [CXCL10]; muscle damage (troponin I [cardiac, fast skeletal, slow skeletal], troponin T, creatine kinase MM isoenzyme [CK-MM], creatine kinase MB isoenzyme [CK-MB], creatine kinase [total], creatine phosphate, and creatinine); and muscle regeneration (myostatin and follistatin)
- DMD Upper Limb Patient-Reported Outcome Measures (DMD UL-PROM)
- Pediatric Outcomes Data Collection Instrument (PODCI)
- DMD Lifetime Mobility Scale (DMD-LMS)
- Resource utilization including the incidence of hospitalizations for orthopedic injury or surgery, pulmonary infections, and antibiotic usage
- Ambulatory subjects only
 - 10-Meter Walk/Run Time (10MWRT)
 - Incidence of loss of ambulation (defined by 10MWRT > 30 seconds)
 - North Star Ambulatory Assessment (NSAA)

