14.5.3. Exploratory Efficacy Endpoints

Exploratory efficacy endpoints will be change from baseline in:

- High-level (shoulder) dimension of the PUL 1.2 at Months 3, 6, 9, and 12;
- High-level (shoulder) dimensions of the PUL 2.0 at Months 3, 6, 9, and 12;
- Mid-level (elbow) dimensions of the PUL 2.0 at Months 3, 6, 9, and 12;
- Distal-level (wrist and hand) dimensions of the PUL 1.2 at Months 3, 6, 9, and 12;
- Distal-level (wrist and hand) dimensions of the PUL 2.0 at Months 3, 6, 9, and 12;
- Grip strength, absolute and percent predicted, at Months 3, 6, 9, and 12;
- Tip-to-tip pinch strength, absolute and percent predicted at Months 3, 6, 9, and 12;
- Key pinch strength, absolute and percent predicted at Months 3, 6, 9, and 12;
- Elbow flexion strength, absolute and percent predicted, at Months 3, 6, 9, and 12;
- DMD UL-PROM at Months 3, 6, 9, and 12;

- PODCI scales (subject and parent) at Months 3, 6, 9, and 12;
- DMD-LMS at Months 3, 6, 9, and 12;
- NSAA at Months 3, 6, 9, and 12;
- 10MWRT at Months 3, 6, 9, and 12;
- Incidence of loss of ambulation (10MWRT > 30 seconds) at Months 3, 6, 9, and 12;
- Pulmonary function tests (absolute and percent predicted [if available]) at Months 3, 6, 9, and 12;
- LV structure and function as assessed by cardiac MRI at Months 6 and 12;
- Biomarkers, which may include osteopontin, IL-1 β , IL-2, IL-6, IL-10, TNF- α , CXCL10, troponin I (cardiac, fast skeletal, slow skeletal), troponin T, CK-MM, CK-MB, creatine kinase (total), creatine phosphate, creatinine, myostatin, and follistatin at Months 3, 6, 9, and 12;
- Resource utilization, including hospitalizations for orthopedic injury or surgery and for pulmonary infections, over the course of the trial.

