14.6. Statistical Methods

Comparisons between treatment groups on efficacy endpoints will be done using repeated measures linear models. Other analyses may also be done using appropriate parametric or non-parametric methods, depending on distributions of the data and whether or not model assumptions are met. An algorithm detailing the decision-making process for performing the primary efficacy analysis, in light of features of the data that cannot be known until the data are observed (e.g., outliers), will be detailed in the SAP.

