6.3.8 Cardiac MRI

LV structure and function as assessed by cardiac MRI include the following parameters:

- LV (myocardium) mass
- LV end-systolic volume
- LV end-systolic volume index
- LV end-diastolic volume
- LV end-diastolic volume index
- LV stroke volume
- LV ejection fraction
- systolic wall thickening (anterior LV, lateral LV, inferior LV, septal LV)
- regional wall motion [dyssynchrony index, circumferential uniformity ratio estimate (CURE)]
- circumferential strain (global, anterior LV, lateral LV, inferior LV, septal LV)
- LV wall thickness
 - end-systolic wall thickness average (anterior, lateral, inferior, septal)
 - end-diastolic wall thickness average (anterior, lateral, inferior, septal)

In addition, the LV mass index (g/m²) will be calculated as

$$\text{LV Mass Index (g/m}^2\text{)} = \text{LV Mass (g)}/\text{BSA (m}^2\text{)}$$

where Body Surface Area (BSA) = 0.007184 * Height (cm)^{0.725} * Weight (kg)^{0.425}. Height and weight measurements closest to the MRI scan will be used. The standing height will be used, if provided; otherwise, the height from ulna length will be used.

All observed values will be displayed in subject listings. Observed values and changes from baseline will be summarized for all parameters except LV wall thickness.

Using the model defined in Section 6.1, the comparisons of interest will be the contrasts between CAP-1002 and placebo at Months 6 and 12 for change from baseline in all parameters except LV wall thickness.

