8 DEVIATIONS FROM STATISTICAL METHODS IN THE PROTOCOL

This final version 3.0 of the statistical analysis plan (SAP) supersedes all previous versions.

There were no changes to the conduct of the study since the last protocol amendment. Analyses planned but not performed and the rationales for the changes are as follows.

The following exploratory efficacy endpoints will not be analyzed:

- High-level (shoulder) dimension of the PUL 1.2;
- Distal-level (wrist and hand) dimension of the PUL 1.2;
- High-level (shoulder) dimension of the PUL 2.0;
- Distal-level (wrist and hand) dimension of the PUL 2.0;
- Grip strength, percent predicted, at Months 3, 6, 9, and 12;
- Tip-to-tip pinch strength, percent predicted, at Months 3, 6, 9, and 12;
- Key pinch strength, percent predicted, at Months 3, 6, 9, and 12;
- Elbow flexion strength, percent predicted, at Months 3, 6, 9, and 12;
- PODCI scales (subject and parent) at Months 3, 6, 9, and 12;
- Parent/caretaker-reported DMD-LMS at Months 3, 6, 9, and 12;
- NSAA at Months 3, 6, 9, and 12;
- 10MWRT at Months 3, 6, 9, and 12;
- Incidence of loss of ambulation (10MWRT > 30 seconds) at Months 3, 6, 9, and 12;
- Biomarkers at Months 3, 6, 9, and 12;
- Resource utilization, including hospitalizations for orthopedic injury or surgery and for pulmonary infections, over the course of the trial.

Originally, it was planned to perform a supportive analysis of the primary efficacy endpoint on the mITT Population. However, it was discovered that the mITT Population is equivalent to the ITT Population, so analyses of efficacy will only be performed on the ITT and PP populations.

Also, originally, it was planned to perform the secondary and exploratory efficacy endpoint analyses on the PP population only. However, it was decided that the same model will be used for the secondary and exploratory endpoints as in the primary efficacy endpoint, so the analyses will be done on the ITT Population as well for all efficacy endpoints except DMD-LMS.

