2.6. Protocol-Specified Endpoints Previously Removed from Analysis

The final version 3.0 of the statistical analysis plan removed some protocol-specified exploratory endpoints from the final analysis. This Addendum reinstates the following exploratory efficacy endpoints for analysis:

- High-level (shoulder) dimension of the PUL 1.2;
- Distal-level (wrist and hand) dimension of the PUL 1.2;
- High-level (shoulder) dimension of the PUL 2.0;
- Distal-level (wrist and hand) dimension of the PUL 2.0;
- Grip strength, percent predicted, at Months 3, 6, 9, and 12;
- Tip-to-tip pinch strength, percent predicted, at Months 3, 6, 9, and 12;
- Key pinch strength, percent predicted, at Months 3, 6, 9, and 12;
- Elbow flexion strength, percent predicted, at Months 3, 6, 9, and 12;
- Pediatric Outcomes Data Collection Instrument (PODCI) scales (subject and parent) at Months 3, 6, 9, and 12;
- Parent/caretaker-reported DMD Lifetime Mobility Scale (DMD-LMS) at Months 3, 6, 9, and 12;

- North Star Ambulatory Assessment (NSAA) at Months 3, 6, 9, and 12;
- Biomarkers at Months 3, 6, 9, and 12.

All PUL and strength endpoints above will be analyzed using summary statistics, the primary MMRM, and the percentile ranked model described above for the ITT and PP Populations. All available data listed for the ITT population.

CK Isoenzyme biomarkers will be analyzed similarly but for the safety population, with all available data listed for the safety population within the serum chemistry laboratory listing.

Other biomarkers will be analyzed only using the percentile ranked model for the ITT population, with all available data listed for the ITT population.

PODCI, parent/caretaker-reported DMD-LMS, and NSAA endpoints above will be listed for the ITT Population.

The following exploratory efficacy endpoints will not be reinstated:

- 10-Meter Walk/Run Time (10MWRT) at Months 3, 6, 9, and 12;
- Incidence of loss of ambulation (10MWRT > 30 seconds) at Months 3, 6, 9, and 12;
- Resource utilization, including hospitalizations for orthopedic injury or surgery and for pulmonary infections, over the course of the trial.

3. Safety Analyses

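### Six protocol-named exploratory measures (SVC, FEV1, MIP, MEP, PCF and LV wall thickness) get no summary or treatment contrast in the final SAP, and its account of analyses not performed omits them

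*SAP*

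**What the plan says.** Protocol 7.2.3 names eight pulmonary measures as exploratory endpoints: SVC, FEV1, FVC, PEF, MIP, MEP, PCF and IFR. It also names six cardiac MRI measures: ejection fraction, end-diastolic volume, end-systolic volume, stroke volume, regional wall thickness and circumferential strain. Protocol 14.5.3 sets the planned times: "Pulmonary function tests (absolute and percent predicted [if available]) at Months 3, 6, 9, and 12", and Months 6 and 12 for cardiac MRI. Protocol 14.6 gives the method: "Comparisons between treatment groups on efficacy endpoints will be done using repeated measures linear models".

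SAP 6.3.7 keeps the full list for measurement ("Pulmonary function tests (PFTs) will measure SVC, FVC, FEV₁, PEF, MIP, MEP, PCF, and IFR") and for subject listings. For summaries it is narrower: "Observed absolute values and changes from baseline will be summarized for FVC, PEF, and IFR". The treatment contrasts cover the same three measures. For cardiac MRI, SAP 6.3.8 says: "Observed values and changes from baseline will be summarized for all parameters except LV wall thickness". It makes the same exception for the model.

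SAP 8 presents itself as the account of planned analyses not performed, with rationales. Under "The following exploratory efficacy endpoints will not be analyzed" it gives 15 items. Addendum 2.6 returns to those items and sorts them into reinstated and not reinstated. Of the reinstated ones it says: "PODCI, parent/caretaker-reported DMD-LMS, and NSAA endpoints above will be listed for the ITT Population".

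**The concern.** Six measures that the protocol planned to compare between arms have lost that comparison, and the section meant to record such losses does not mention them. A reader who checks SAP 8 and then the addendum, which says that it restores endpoints for completeness, would conclude that every removal is accounted for.

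The setting makes this matter. SAP 3.3 describes four completed interim analyses, the last three with the stated aim of evaluating unblinded efficacy. Protocol 9.5 says that designated sponsor personnel were unblinded to assignments and aggregate results after the first. When a plan finalised at that stage carries forward three of eight respiratory measures without a reason, readers cannot judge whether the three represent the respiratory data as a whole.

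A smaller point concerns PODCI, caretaker-reported DMD-LMS and NSAA. The addendum describes them as reinstated for analysis, but they receive only a listing.

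**Working it through.** The check compares sets of endpoints; no power or error-rate formula applies.

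**Inputs.** Protocol 7.2.3, 14.5.3 and 14.6; SAP 6.3.4 to 6.3.8; SAP 8; Addendum 2.6.

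| Measure | Protocol endpoint | SAP listing | SAP summary and model | In SAP 8 list | In Addendum 2.6 |
|---|---|---|---|---|---|
| FVC, PEF, IFR | yes | yes | yes | not needed | not needed |
| SVC, FEV1, MIP, MEP, PCF | yes | yes | no | no | no |
| LV wall thickness | yes | yes | no | no | no |

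**Pulmonary.** 8 named − 3 summarised and modelled = 5 omitted; 5/8 = 62.5%. None of the 5 is in SAP 8 or Addendum 2.6.

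**Cardiac MRI.** 1 of the 6 measures named in Protocol 7.2.3 is omitted, and it too is in neither list. Meanwhile SAP 6.3.8 models parameters that Protocol 7.2.3 does not name, such as LV mass and the dyssynchrony index.

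**Total.** 5 + 1 = 6 measures.

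**Is the account closed without them?** SAP 8 has 15 items. Addendum 2.6 reinstates 12 and declines to reinstate 3, and 12 + 3 = 15, item for item. The two lists therefore reconcile with each other but not with the protocol.

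**Listing-only reinstatement.** Of the 12 items reinstated for analysis, 3 (PODCI, caretaker-reported DMD-LMS, NSAA) are then only listed. SAP 6.3.4, 6.3.5 and 6.3.6 already provided listings for all three, so the reinstatement adds nothing for them.

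**Timing.** The current protocol describes the first interim analysis as already performed and still carries all eight pulmonary measures and wall thickness. SAP version 3.0 describes all four looks in the past tense. The restriction therefore stands in a plan finalised after the looks. When it was first written cannot be read from the documents.

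**The case against.** The strongest reply is that nothing is hidden. SAP 6.3.7 says which tests are listed, summarised and modelled, and SAP 6.3.8 states the wall-thickness exception twice. All values stay in subject listings. That stands: the gap is the missing reason and the missing entry in SAP 8. Calling the restriction concealed would go too far.

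A reader might also infer that the measures were dropped because of what the unblinded looks showed. The documents do not support this. Earlier SAP versions are not available, the interim dates and the appendices of tables are redacted, and a plan written before the first look may already have had the same restriction. Nor do the documents show that anyone saw the omitted measures by arm.

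Other tempting readings also fail:

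- Quality of life does not go without a between-arm estimate. SAP 6.3.3 models DMD UL-PROM by domain and in total, and SAP 6.3.5 models two DMD-LMS domains.
- The removal of PODCI is declared in SAP 8; only the addendum's wording is wrong.
- The secondary cardiac endpoint is not affected. Regional systolic wall thickening is a different measure from wall thickness and is still modelled.
- A count of lost contrasts would be artificial. The protocol plans percent predicted values only where available and names wall thickness as one item.

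It can also be said that the addendum covers the six measures, since its Section 2 calls the MMRM the pre-specified analysis for all endpoints. That contradicts SAP 6.3.7 and 6.3.8, and the addendum's own rank model extends only to some exploratory endpoints, which it does not name. The protocol's promise to justify deviations (14.1) concerns departures from the SAP, whereas here the SAP departs from the protocol.

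Finally, the consequence is limited. Protocol 14.6.1 makes no multiplicity adjustment for exploratory endpoints, and SAP 4.4 treats p-values after the first interim analysis as nominal. This stands and sets the weight of the point.

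**Conclusion.** The point holds as a matter of selective reporting. Six protocol-named exploratory measures (5 of 8 pulmonary, 1 of 6 cardiac MRI) have no by-arm summary and no treatment contrast in a SAP finalised after four interim analyses. No reason is given, and they are absent from both lists that are supposed to account for removed analyses. In addition, 3 of the 12 endpoints described as reinstated for analysis are only listed.

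This rests on reading Protocol 14.6 as applying to exploratory as well as primary and secondary efficacy endpoints, which its wording supports, and on taking SAP 8 as intended to be complete. It does not rest on any claim about motive or about when the choice was made. Inference on the primary endpoint and its type I error are not affected. The change should be made, but the trial's main conclusions do not depend on it.

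**What to change.** Add SVC, FEV1, MIP, MEP, PCF and LV wall thickness to the by-arm summaries and to the Section 6.1 MMRM, at Months 3, 6, 9 and 12 for the pulmonary tests and Months 6 and 12 for wall thickness. Label the results exploratory and nominal.

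Correct SAP 8 and Addendum 2.6 so that any measure still not analysed is named, with the reason and the date of the decision.

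For PODCI, caretaker-reported DMD-LMS and NSAA, either change the addendum to say that they are listed or give descriptive by-arm summaries. A PODCI model is not required: Protocol 11.8.3 describes forms validated by age band up to 18 years, and the inclusion criteria set no upper age limit.

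The cost is a few more tables, using data already due to be collected and a model already specified, plus some lines of text. The drawback is more unadjusted p-values in a trial of 20 subjects, which the labelling should make plain.

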6.3.8 Cardiac MRI

LV structure and function as assessed by cardiac MRI include the following parameters:

- LV (myocardium) mass
- LV end-systolic volume
- LV end-systolic volume index
- LV end-diastolic volume
- LV end-diastolic volume index
- LV stroke volume
- LV ejection fraction
- systolic wall thickening (anterior LV, lateral LV, inferior LV, septal LV)
- regional wall motion [dyssynchrony index, circumferential uniformity ratio estimate (CURE)]
- circumferential strain (global, anterior LV, lateral LV, inferior LV, septal LV)
- LV wall thickness
 - end-systolic wall thickness average (anterior, lateral, inferior, septal)
 - end-diastolic wall thickness average (anterior, lateral, inferior, septal)

In addition, the LV mass index (g/m²) will be calculated as

$$\text{LV Mass Index (g/m}^2\text{)} = \text{LV Mass (g)}/\text{BSA (m}^2\text{)}$$

where Body Surface Area (BSA) = 0.007184 * Height (cm)^{0.725} * Weight (kg)^{0.425}. Height and weight measurements closest to the MRI scan will be used. The standing height will be used, if provided; otherwise, the height from ulna length will be used.

All observed values will be displayed in subject listings. Observed values and changes from baseline will be summarized for all parameters except LV wall thickness.

Using the model defined in Section 6.1, the comparisons of interest will be the contrasts between CAP-1002 and placebo at Months 6 and 12 for change from baseline in all parameters except LV wall thickness.

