⁵ A blood sample for tryptase should be obtained within 3 hours of the onset of allergic signs or symptoms, and a second red top tube should be drawn within 3 hours of a severe allergic reaction, and frozen at -20°C, for other future analyses.

⁶ All IP infusions will be conducted in an outpatient setting at the investigative site. Prior to each IP infusion, medications will be administered to the subject as determined by the Investigator based on the pre-treatment guidelines provided by Capricor and/or institutional protocols to minimize the risk of potential severe allergic reactions such as anaphylaxis. Subjects will be observed for at least 2 hours post infusion, including pulse oximetry monitoring for at least 30 minutes post infusion. Sites will observe local institutional policies related to parenteral infusions and post-infusion monitoring.

⁷ A safety phone call will be performed 14 days (± 3 days) after each IP infusion, and if clinically indicated, an unscheduled in-person visit will be performed at the investigative site with targeted assessments based on presentation of signs and symptoms.

⁸ Ulna length will be measured in all subjects. Standing height will be measured if a subject is capable. If standing height cannot be measured, height will be calculated using a measurement of ulna length per Section 13.1.2.

⁹ Paired forced-maneuver testing will be performed on Screening Day 1 and Day 2 (approximately 24 hours between testing sessions) to confirm acceptable FVC variance (exclusion criterion 7). PFT testing sequence: SVC, forced maneuver (FEV₁/FVC/PEF), MIP, MEP, PCF, and IFR.

¹⁰ Blood collections for clinical laboratory and DSA testing at Week 4 and pre-dose DSA testing at Months 3, 6, and 9 will occur either at the investigative site or remotely at a designated central laboratory patient service center.

¹¹ Blood and urine samples will be collected using trial-specific laboratory kits, and then shipped to and tested at a central laboratory. Required sample collection for a visit may occur on multiple days; if the visit includes an IP infusion, sample collections should occur prior to IP administration. Baseline blood samples may be collected on Day 1 prior to IP administration to reduce number of venipunctures.

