13.1.2. Weight and Height

Weight, ulna length, and standing height measurements will be performed.

Investigative sites will make every effort to perform a weight measurement without the subject's wheelchair or other assistive device (e.g., walker), if applicable.

Ulna length will be measured in all subjects. Standing height will be measured if a subject is capable. If standing height cannot be measured, height will be calculated using the subject's ulna length ([Gauld et al., 2004](#)). It is critical to reduce variability in ulna length and standing height measurements across investigative sites. Therefore, site personnel must complete trial-specific training prior to measuring a subject's ulna length and standing height.

Table 5: Height Calculation from Ulna Length

$$\begin{aligned}\text{Height (cm)} = & [4.605 \times \text{Ulna Length (cm)}] \\ & + [1.308 \times \text{Age (years)}] \\ & + 28.003\end{aligned}$$

Centimeter and year entries must include decimal places. If a subject is 18 years or older, enter "18" in the formula for age.

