7.4 Vital Signs, Height, Weight and BMI

Vital signs will include systolic and diastolic blood pressure, heart rate, respiratory rate, body temperature and pulse oximetry (SpO₂). Pre-infusion observed values and changes from baseline will be summarized at each post-baseline visit. Scheduled assessments will be summarized, and unscheduled events will only be listed.

Listings of vital signs, ulna length, height, weight, and BMI will be provided. Height will either be measured (i.e., standing height) or calculated from the subject's ulna length.

7.5 12-Lead Electrocardiograms

All 12-lead electrocardiogram (ECG) results will be displayed in subject listings.

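### LV mass index: the SAP lets the height source change between scans within a subject, so a change score can mix standing and ulna-derived height

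*SAP*

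**What the plan says.** For LV mass index, SAP 6.3.8 divides LV mass by a body surface area computed from height and weight. On timing it says "Height and weight measurements closest to the MRI scan will be used"; on source it says "The standing height will be used, if provided; otherwise, the height from ulna length will be used." The same section then compares the arms on change from baseline at Months 6 and 12 for all cardiac MRI parameters except LV wall thickness. LV mass index is introduced in that section and is not excepted.

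The general rule is in protocol 13.1.2, "If standing height cannot be measured, height will be calculated using the subject's ulna length", and in footnote 8 to protocol Table 3: "Ulna length will be measured in all subjects. Standing height will be measured if a subject is capable." Table 3 schedules height and ulna length together at Screening, Baseline and Months 3, 6, 9 and 12. Cardiac MRI is scheduled at Screening, Month 6 and Month 12. SAP 7.4 repeats the either-or rule for listings: "Height will either be measured (i.e., standing height) or calculated from the subject's ulna length."

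For lung function, SAP 6.3.7 models "FVC, absolute value and percent predicted", and likewise PEF, at Months 3, 6, 9 and 12. It names neither the reference equation nor the height that enters it.

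**The concern.** A change from baseline is clean only if both ends are measured in the same way. Under SAP 6.3.8 the height method is picked separately for each scan. If a subject has a standing height near the Screening scan and none near Month 6 or Month 12, the two body surface areas rest on different methods. Any systematic gap between the methods then passes into the change in LV mass index as if the heart had changed.

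The switch would not happen at random. Its natural trigger is losing the ability to stand, which is disease progression and could in principle differ by arm. It is also avoidable, because ulna length is to be measured in every subject whenever height is scheduled.

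**Working it through.** The plan gives no figure to reproduce here, so the check is a sensitivity calculation.

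**Inputs from the documents**
- BSA = 0.007184 × H^0.725 × W^0.425, and LV mass index = LV mass / BSA (SAP 6.3.8).
- Ulna-derived height = 4.605 × ulna (cm) + 1.308 × age (years) + 28.003, with age entered as 18 from 18 upwards (protocol Table 5).
- 20 subjects randomized 1:1, so about 10 per arm (protocol 7.4 and 14.2).

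**Assumptions, not in the documents**
- Standing height 145 cm; ulna-derived height differs from it by 2 to 6 cm in either direction.
- For percent predicted only: predicted value proportional to height to the power 2 to 3, and a true value of 60% predicted.

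**LV mass index.** With LV mass and weight unchanged, a switch multiplies the index by (H_ulna / H_standing)^−0.725.

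| Gap (ulna minus standing) | BSA ratio | Shift in LV mass index |
|---|---|---|
| +2 cm | (147/145)^0.725 = 1.010 | −1.0% |
| +6 cm | (151/145)^0.725 = 1.030 | −2.9% |
| −2 cm | (143/145)^0.725 = 0.990 | +1.0% |
| −6 cm | (139/145)^0.725 = 0.970 | +3.1% |

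One switcher among 10, with an index near the arm mean, moves that mean by a tenth of this, about 0.1% to 0.3%. Only subjects able to have an MRI contribute, so the divisor could be smaller than 10. With no switchers the effect is zero.

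**Percent-predicted FVC or PEF, only if the same height rule feeds them.**
- Ulna height larger: 60 × (145/147)^2 = 58.4, a shift of −1.6 points, to 60 × (145/151)^3 = 53.1, a shift of −6.9 points.
- Ulna height smaller: 60 × (145/143)^2 = 61.7, a shift of +1.7 points, to 60 × (145/139)^3 = 68.1, a shift of +8.1 points.
- Per switcher in an arm of 10, the mean moves by about 0.2 to 0.8 points in one direction or the other.

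**Error in ulna-derived height itself.**
- An assumed 0.5 cm error in ulna length moves height by 4.605 × 0.5 = 2.3 cm. At 145 cm the index changes by the factor (147.3/145)^−0.725, about −1.1%.
- Below age 18 the formula adds 1.308 cm over a year even with no change in ulna length. At 145 cm that is (146.308/145)^−0.725, about −0.6%.

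Both are of the order of the lower end of the switching artefact.

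**With one method per subject**, the switching term is zero. Measurement error and true growth remain.

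**The case against.** The case against giving this much weight is strong, and most of it stands.

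- **Lung function.** A reader might infer that percent-predicted FVC and PEF shift by artefact whenever a subject stops standing. The documents do not show this. The quoted rule governs body surface area for LV mass index. SAP 6.3.7 is silent on the height input, and protocol 11.4 leaves technique and requirements to a core-lab manual that is not among the documents. That manual may already fix one height per subject.
- **How many switch.** A reader might take the loss-of-ambulation endpoint as evidence that switches are expected. Loss of ambulation is defined by a 10-meter time above 30 seconds, and inclusion criterion 6 does not count standing unassisted as ambulation. A subject can therefore lose ambulation and still be measured standing. Subjects who cannot stand at entry have ulna-derived height throughout and are unaffected.
- **Bias for or against CAP-1002.** A reader might infer a biased treatment contrast. That needs switchers, a non-zero gap and an imbalance between arms. None of these is in the documents, and the sign reverses with the gap.
- **Consequence.** No primary or secondary efficacy endpoint uses height. SAP 4.4 treats p-values after the interim analysis as nominal. Unindexed LV mass and absolute FVC and PEF go through the same model, so an artefact should show as disagreement between paired results.
- **Ulna height for everyone.** This is not a free remedy, as the formula errors above show. It would bring that error to subjects who can be measured standing at every scan.

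What the objection does not remove is the rule itself. For LV mass index the source is chosen scan by scan, and no other section of either document holds it fixed.

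**Conclusion.** The point holds for LV mass index, as a minor gap. SAP 6.3.8 as written allows two height methods inside one change score. For an affected subject the shift is about 1% to 3% of LV mass index, assuming a 2 to 6 cm gap at 145 cm, with direction set by the sign of the gap. The number of affected subjects is unknown and may be zero.

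For percent-predicted FVC and PEF the supported conclusion is narrower. The height input is not stated, so the same problem is possible but not shown. The two LV volume indices listed in SAP 6.3.8 are in the same position, because the SAP does not say how they are indexed. The primary endpoint, the secondary endpoints, absolute FVC and PEF, LVEF and unindexed LV measures are not touched.

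**What to change.** In SAP 6.3.8, replace the scan-by-scan choice with one method per subject at all scans: standing height if it is available at every scan used for that subject, otherwise ulna-derived height at every scan. In SAP 6.3.7, state the reference equation and height input for percent-predicted FVC and PEF, and apply the same within-subject rule to that height. Add a listing of any subject whose available height source changed. If that listing is empty, the matter is closed.

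The cost is a few lines of SAP text, one listing and, if anyone switched, a small recomputation from data already scheduled for collection. The core lab may need to recompute percent predicted for those subjects. The downside is that a subject who could stand at only some visits loses the standing measurements in favour of a less exact ulna-derived height. Subjects with standing height at every scan keep it.
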